#### **4.3 Patient Population**

This study will enroll adult male and female patients of age  $\geq$  18 years with metastatic or advanced, unresectable solid tumor types, who have progressed or recurred following standard of care (SOC) therapies, or are ineligible for, or refuse, other safe and effective SOC treatment.

#### **4.4 End of Study**

The end of the study is defined as the date of the last visit of the last patient participating in the trial.

#### **4.5 Duration of Therapy**

Upon completion of the first two treatment cycles (i.e., 4 weeks, with at least 2 doses of PTX-35), in the absence of disease progression and unacceptable toxicity, patients may continue to be treated with PTX-35 at the same dose and schedule until disease progression, death, patient's withdrawal of consent, Investigator's decision to remove patient, or intolerable toxicity, whichever occurs first.

At the discretion of the Investigator, and in the absence of clinical deterioration, treatment with PTX-35 may continue beyond initial evidence of radiological progression as per Section 8.2.1.

## 4.6 Trial Discontinuation

For reasonable cause, either the Investigator or the Sponsor may terminate this study prematurely. Written notification of the termination is required. Conditions that may warrant termination include, but are not limited to:

- The discovery of an unexpected, significant, or unacceptable risk to the patients enrolled in the study.
- Failure of the Investigator to enter patients at an acceptable rate.
- Insufficient adherence to protocol requirements (non-compliance).
- Lack of evaluable and/or complete data.
- Decision to modify the developmental plan of the drug.
- A decision on the part of the Sponsor to suspend or discontinue development of the drug.

Section [5.5](#) Study Stopping Criteria lists events that warrants immediate stop of treatment until reviewed by the Safety Review Committee. This assessment may also result in trial discontinuation (equivalent to first bullet above).

## 4.7 Investigational Product Accountability/Disposition of Clinical Trial Supplies

Investigational Product (IP) accountability records will be maintained for all clinical trial supplies.

All unused clinical trial supplies will be destroyed per the institution's standard operating procedure, or returned to the Sponsor or designee. Destruction and/or return of IP and trial supplies must be documented, and the documentation will be reviewed by/sent to the Sponsor or their Designee.

## 5.0 SELECTION AND WITHDRAWAL OF PATIENTS

### 5.1 Inclusion Criteria

Patients **must** meet all of the following inclusion criteria before they will be allowed to participate in the trial:

1. Be willing and have the capacity to sign the written informed consent form.
2. Be male or female of at least 18 years of age at the time of signing informed consent.
3. Have a documented diagnosis of metastatic or advanced, unresectable solid tumor disease. Patient must have progressed or recurred following standard of care (SOC) therapies, or are ineligible for, or who refuse, other safe and effective SOC therapies, and whom the Investigator believes may benefit from experimental treatment with PTX-35.

4. Have an acceptable organ function, as defined below:
  - a. Albumin  $\geq$  2.5 g/dL
  - b. Total bilirubin  $< 3.0 \times$  upper limit of normal (ULN) unless patient has Gilbert's syndrome.
  - c. Alanine transaminase (ALT) and aspartate transaminase (AST)  $\leq 3.0 \times$  ULN, or  $\leq 5 \times$  ULN in the case of liver metastases.
  - d. Calculated or measured creatinine clearance  $> 35$  mL/minute per the Cockcroft-Gault formula.
  - e. Absolute neutrophil count  $\geq 1,500/\text{mm}^3$
  - f. Hemoglobin  $\geq 9$  g/dL.
  - g. Platelet count  $\geq 100,000/\text{mm}^3$
5. Have an Eastern Cooperative Oncology Group (ECOG) performance status of 0 to 2 ([APPENDIX I](#)).
6. Have life expectancy of at least three months.
7. Patients, both females and males, of childbearing/reproductive potential must agree to use adequate contraception, or continuous abstinence, while included in the trial and for six months after the last treatment with PTX-35.

## 5.2 Exclusion Criteria

Patients **MUST NOT** enter the trial if they meet any of the following exclusion criteria:

1. Have received any systemic anticancer therapy including small molecules, chemotherapy, radiation therapy, monoclonal antibodies or any other experimental drug within 4 weeks of first dose of PTX-35. Adjuvant anti-hormonal treatment(s) for prior breast cancer or prostate cancer are allowed. (Note: washout for palliative radiation therapy is 2 weeks).

2. Have clinically significant cardiac disease, including:
  - a. Onset of unstable angina within 6 months of signing the Informed Consent Form (ICF).
  - b. Acute myocardial infarction within 6 months of the signing the ICF.
  - c. Known congestive heart failure (Grade III or IV as classified by the New York Heart Association); and/or a known decreased cardiac ejection fraction (LVEF) of < 45%.
  - d. Uncontrolled hypertension defined as systolic blood pressure ≥160 mmHg and/or diastolic blood pressure ≥ 100 mmHg, despite optimal medical management.
3. Known or clinically suspected leptomeningeal disease. Stable, previously treated metastases in the brain or spinal cord, are allowed as long as these are considered stable (by CT or MRI), and not requiring systemic corticosteroids.
4. Have a history of ≥ Grade 3 allergic reactions, or suspected allergy or intolerance to monoclonal antibody therapies.
5. Have a history of suspected cytokine release syndrome (CRS).
6. Have any known immunodeficiency disorders (testing not required).
7. Have received prior allogeneic stem cell transplant.
8. Have ongoing or current autoimmune disease. Permanent but stable and manageable immune related adverse events (irAE) from prior therapies are permissible if prednisone equivalent corticosteroid use does not exceed 10 mg/day.
9. Have any other condition requiring concurrent systemic immunosuppressive therapy (other than allowable exceptions which do not exceed 10mg/day of prednisone/corticosteroid use).
10. Have clinically significant active viral, bacterial or fungal infection requiring:
  - a. Intravenous treatment with antimicrobial therapy completed less than two weeks prior to first dose, or
  - b. Oral treatment with antimicrobial therapy completed less than one week prior to first dose.
11. Have had major surgery (requiring general anesthesia or inpatient hospitalization) within four weeks before first administration of PTX-35.

12. Have had a known tetanus/diphtheria vaccine within the past 10 years.
13. Have known additional malignancy that is active and/or progressive requiring treatment; exceptions include basal cell or squamous cell skin cancer, *in situ* cervical cancer, or other cancer for which the patient has been disease-free for at least two years.
14. Have known previously untreated or symptomatic metastases in the brain or spinal cord requiring steroids. Patients with treated and stable CNS metastases may be enrolled after approval of the sponsor and/or Medical Monitor.
15. Have any other ongoing significant, uncontrolled medical condition in the opinion of the Investigator.
16. Have known positive serology for human immunodeficiency virus (HIV), hepatitis B, or hepatitis C (except in cases of immunity after cured infection). Testing not required.
17. Have a history of substance abuse, medical, psychological or social conditions that may interfere with the patient's participation in the trial or evaluation of the trial result.
18. Be a female patient who is pregnant or breast feeding.

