### **Footnotes to Schedule of Assessments**

- a. Within 28 days prior to study treatment initiation.
- b. Within 7 days prior to study treatment initiation.
- c. If performed within 3 days of Cycle 1 Day 1, these tests do not need to be repeated unless clinically indicated.
- d. Vital signs, including blood pressure, heart rate, respiration rate, and temperature. During Cycle 1 and 2: prior to PTX-35 administration and at 30 min ( $\pm 5$  min) and 1h ( $\pm 5$  min) after end of PTX-35 infusion. Other cycles: only prior to PTX-35 administration.
- e. 12-lead ECGs (in triplicate) to be performed with patient in a semi-recumbent position at screening and on Day 1 of each cycle prior to PTX-35 administration.
- f. Tumor measurement per RECIST 1.1. Baseline tumor assessment should be performed within 28 days prior to study treatment initiation. Patients will be evaluated every 8 weeks ( $\pm 1$  week) from C1D1 until disease progression, regardless of dose delays.
- g. Hematology, including hemoglobin, WBC with differential, and platelet count (Approximately 5 mL blood per draw).
- h. Serum chemistry including: sodium, potassium, chloride,  $\text{CO}_2$ , BUN, creatinine, glucose, calcium, albumin, total protein, total bilirubin, AST, ALT, alkaline phosphatase, TSH (Approximately 5 mL blood per draw).
- i. For women of childbearing potential only, a negative serum or urine  $\beta$ -hCG must be documented within 7 days prior to first dose of PTX-35.
- j. PTX-35 is administered as an IV infusion. Each patient must remain in clinic for a 6-hour safety observation period after the end of the PTX-35 infusion unless the SRC reduces the required observation period.
- k. HLA sample will be collected pre-dose at Cycle 1 only.
- l. PK samples will be collected at the following timepoints: pre-dose; 30min ( $\pm 5$ min), 2hr ( $\pm 5$ min), 4hr ( $\pm 5$ min), 24hr ( $\pm 2$ hr), 72hr ( $\pm 2$ hr), 144hr ( $\pm 2$ hr), 216hr ( $\pm 2$ hr) after end of PTX-35 infusion for Cycles 1 and 2, and pre-dose at Cycle 3 only.
- m. Cytokine blood sample collection at the following timepoints during Cycle 1 and 2: prior to PTX-35 administration and at 2 hr ( $\pm 5$ min) after end of PTX-35 infusion. Collection at cycle 3 and beyond is only required if the patient is symptomatic (i.e., flu-like or allergic reactions) prior to PTX-35 infusion and at 2 hr ( $\pm 5$ min) after end of PTX-35 infusion.

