## **8.2 Efficacy Assessments**

Patient's disease status will be monitored by clinical and radiological assessment (CT scans or MRI) as per RECIST 1.1 criteria where applicable. Patient response per RECIST 1.1 will be evaluated as complete response, partial response, stable disease, or progressive disease.

For the purpose of this study, patients will be evaluated after every 8 weeks  $\pm$  1-week from C1D1, regardless of any delays in treatment cycles. In the event objective response (PR or CR) is noted, changes in tumor measurements must be confirmed by repeat assessments that should be performed at least 4 weeks after the criteria for response are first met. For stable disease (SD), follow-up measurements must meet the SD criteria at least 6 weeks after study entry.

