## APPENDIX II - Tumor Measurement Based on RECIST 1.1 Criteria

See the international criteria proposed by the Response Evaluation Criteria in Solid Tumors (RECIST) Committee, version 1.1 for additional details on RECIST 1.1.

Measurable disease will be defined as the presence of at least one measurable lesion that can be accurately measured in at least one dimension with the longest diameter a minimum size of:

- >10mm by CT scan (CT scan slice thickness no greater than 5 mm)
- 10mm caliper measurement by clinical exam (lesions which cannot be accurately measured with calipers should be recorded as non-measurable).
- 20 mm by chest X-ray.

For malignant lymph nodes to be considered pathologically enlarged and measurable, a lymph node must be  $\geq 15$ mm in short axis when assessed by CT scan (CT scan slice thickness recommended to be no greater than 5mm). At baseline and in follow-up, only the short axis will be measured and followed.

All other lesions, including small lesions (longest diameter <10mm or pathological lymph nodes with  $\geq 10$  to <15 mm short axis) as well as truly non-measurable lesions, will be considered non-measurable. Lesions considered truly non-measurable include: leptomeningeal disease; ascites; pleural/pericardial effusion; inflammatory breast disease; lymphangitic involvement of skin or lung, abdominal masses/abdominal organomegaly identified by physical exam that is not measurable by reproducible imaging techniques.

All measurements should be recorded in metric notation, using calipers if clinically assessed. All baseline evaluations should be performed as close as possible to the treatment start and never more than 4 weeks before the beginning of the treatment. The same method of assessment and the same technique should be used to characterize each identified and reported lesion at baseline and during follow-up. Imaging based evaluation should always be done rather than clinical examination unless the lesion(s) being followed cannot be imaged but are assessable by clinical exam. Clinical lesions will only be considered measurable when they are superficial and  $\geq 10$  mm diameter as assessed using calipers (e.g., skin nodules). For the case of skin lesions, documentation by color photography including a ruler to estimate the size of the lesions is recommended.

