### *Baseline Documentation of Target and Non-Target Lesions*

All measurable lesions up to a maximum of 5 lesions total (and a maximum of two lesions per organ) representative of all involved organs should be identified as target lesions and will be recorded and measured at baseline.

Target lesions should be selected on the basis of their size (lesions with the longer diameter), be representative of all involved organs, but in addition should be those that lend themselves to reproducible repeated measurements.

A sum of the diameters (longest for non-nodal lesions, short axis for nodal lesions) for all target lesions will be calculated and reported as the baseline sum diameters. If lymph nodes are to be included in the sum, only the short axis is added into the sum. The baseline sum diameters will be used as reference to further characterize the objective tumor response of the measurable dimension of the disease.

All other lesions (or sites of disease) including pathological lymph nodes should be identified as non-target lesions and should also be recorded at baseline. Measurements are not required, and these lesions should be followed as "present" or "absent", or in rare cases "unequivocal progression".

*Evaluation of Target Lesions using RECIST 1.1 Criteria*

NOTE: In addition to the information below, also see section 4.3.2 in the international criteria proposed by the Response Evaluation Criteria in Solid Tumors (RECIST) Committee, version 1.1 for special notes on the assessment of target lesions.

Complete response (CR) – Disappearance of all target lesions. Any pathological lymph node (LN) (whether target or non-target) must have decreased in short axis to <10mm.

Partial response (PR) – At least a 30% decrease in the sum of the LD of the target lesions taking as reference the baseline sum LD.

Progressive Disease (PD) – At least a 20% increase in the sum of the LD of the target lesions taking as reference the smallest sum LD recorded since the treatment started including baseline if that is the smallest on study. In addition to the relative increase of 20%, the sum must also demonstrate an absolute increase of at least 5mm. The appearance of one or more new lesions also constitutes PD.

Stable disease (SD) – Neither sufficient shrinkage to qualify for PR nor sufficient increase to qualify for PD taking as references the smallest sum LD since the treatment started.

*Evaluation of Non-Target Lesions using RECIST 1.1 Criteria*

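### Palliative radiation is allowed until 14 days before first dose while the baseline scan may be 28 days old, so a target lesion can be irradiated after its baseline measurement with no stated rule for handling it

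*Combined protocol and SAP*

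**What the plan says.** **Washout.** Exclusion criterion 1 (5.2, repeated in the Synopsis) rules out anticancer treatment, including radiation, "monoclonal antibodies or any other experimental drug within 4 weeks of first dose of PTX-35". The same criterion then shortens the interval for one kind of treatment: "Note: washout for palliative radiation therapy is 2 weeks".

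**Baseline scan.** Table 2 footnote f states: "Baseline tumor assessment should be performed within 28 days prior to study treatment initiation". Section 7.2 gives the same 28 days. Appendix II asks for baseline evaluations close to the start of treatment and sets the outer limit as "never more than 4 weeks before the beginning of the treatment". None of these places ties the scan to the end of radiation.

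**Target lesions.** Appendix II takes "All measurable lesions up to a maximum of 5 lesions total (and a maximum of two lesions per organ) representative of all involved organs". The selection rule reads: "Target lesions should be selected on the basis of their size (lesions with the longer diameter), be representative of all involved organs"; it adds that lesions should allow repeatable measurement. Appendix II does not mention irradiated lesions. It refers the reader to the RECIST 1.1 publication for further detail and for notes on target lesions.

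**Response.** PR is "At least a 30% decrease in the sum of the LD of the target lesions taking as reference the baseline sum LD". Under 8.2 a CR or PR "must be confirmed by repeat assessments that should be performed at least 4 weeks after the criteria for response are first met". PD is measured from the lowest sum on study, baseline included; new lesions are also PD.

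**The concern.** The 4-week washout matches the 28-day scan window, so a treatment subject to it cannot fall between an eligible scan and first dose. The 2-week washout does not match. A site can scan, irradiate a painful lesion, wait two weeks and dose, with every criterion met. Measured against a pre-radiation baseline, that lesion's shrinkage enters the sum of diameters as if it had happened on PTX-35.

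Preliminary clinical benefit is a stated exploratory objective, read from BOR, PFS and OS in a single-arm trial with 3–6 patients per dose level. There is no control arm in which the same artefact would show. Section 9.8 says that response by dose level or tumor type may lead to an amendment for cohort expansion. The protocol's background (2.1.3) also reports mouse work combining radiation with the parent antibody. A patient irradiated in the gap would in effect supply combined-treatment data recorded as single-agent response.

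**Working it through.** There is no figure in the plan to reproduce: 9.8 says that no sample size was calculated, and all analyses are descriptive. The check is date arithmetic and sum-of-diameters arithmetic.

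**1. Length of the gap.** Inputs: scan window 28 days (Table 2 footnote f, 7.2, Appendix II); washout 14 days for palliative radiation and 28 days otherwise (5.2).
- Palliative radiation: 28 − 14 = 14 days in which it can follow an eligible scan.
- Other radiation: 28 − 28 = 0 days.
- The first on-study scan is at week 8 ± 1, that is 49 to 63 days after C1D1. Radiation ending 14 days before first dose precedes it by 14 + 49 = 63 to 14 + 63 = 77 days.

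**2. Does another provision close the gap?**
- 6.4 bars other anticancer therapy only during study treatment, not between scan and first dose.
- The Efficacy Evaluable Population (9.1) does not exclude such patients.
- Confirmation at 4 weeks or later (8.2) does not remove a lasting radiation effect.
- Appendix II's request for a scan near the start narrows the gap, but the same sentence permits 4 weeks.

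**3. When can one irradiated lesion change the response category?** Assume k equal target lesions (k ≤ 5 by Appendix II), one of them irradiated.
- PR with the others unchanged needs shrinkage s with s/k ≥ 0.30, so s ≥ 0.30k.
- Masking at the first on-study scan, where baseline is the reference: the sum reaches +20% when the others grow by g. If the irradiated lesion is unchanged, g = 0.2k/(k − 1). If it halves (an assumption), g = (1.2k − 0.5)/(k − 1) − 1.

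| k | Shrinkage that gives PR alone | g if lesion unchanged | g if lesion halves |
|---|---|---|---|
| 1 | 30% | – | – |
| 2 | 60% | 40% | 90% |
| 3 | 90% | 30% | 55% |
| 4 | 120% (impossible) | 26.7% | 43.3% |
| 5 | 150% (impossible) | 25% | 37.5% |

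**4. Unequal lesions, one illustration.** Target lesions of 40 mm and 30 mm give a sum of 70 mm. If the 40 mm lesion falls to 18 mm (22/40 = 55%) and the other is unchanged, the sum is 48 mm and the decrease is (70 − 48)/70 = 31.4%. That meets the PR threshold, subject to confirmation.

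**5. The opposite direction.** In the same illustration 48 mm becomes the nadir. PD is then reached at 1.2 × 48 = 57.6 mm (+9.6 mm), against 1.2 × 70 = 84 mm (+14 mm) if the sum had stayed at 70 mm. Both increases exceed the 5 mm absolute minimum.

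**6. Weight of one case.** One spurious responder is 1/3 = 33.3% of a 3-patient cohort and 1/6 = 16.7% of a 6-patient cohort. Across the planned 22–34 patients it is 1/22 = 4.5% to 1/34 = 2.9%.

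**The case against.** The best reply is that RECIST 1.1 itself governs the trial (8.2.1) and Appendix II defers to it for detail, so the silence may be filled there. That cannot be settled from the documents. What stands is that Appendix II restates the target-lesion rules without covering this case. A reader might infer that the irradiated lesion is certain to stay a target lesion; the documents show only that nothing in them prevents it.

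Three further inferences are tempting and not supported:
- *The bias can only favor the drug.* PD is measured from the lowest on-study sum, so a radiation-lowered nadir can bring a later PD call forward (step 5). New lesions and unequivocal non-target progression count as PD whatever the sum does, which also limits masking.
- *Palliative radiation is the only treatment outside the 4-week washout.* The same criterion allows adjuvant anti-hormonal treatment for prior breast or prostate cancer with no washout.
- *A response at one dose level triggers expansion.* Section 9.8 describes a possible amendment. That is discretionary and leaves room to review individual responders.

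It is also fair to say that prior cancer treatments are recorded (7.2) and all patient data are listed (9.0), so such a case might be spotted in a small cohort. That helps interpretation but does not supply the missing post-radiation baseline.

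**Conclusion.** The gap is real and specific: up to 14 days in which an eligible patient's target lesion can be irradiated after its baseline measurement, with no rule in the protocol for what follows. The resulting bias is mainly, but not only, in the drug's favor. A PR from one irradiated lesion alone is possible with one to three equal target lesions and impossible with four or five; with more lesions the effect is toward SD and a later first PD call. One case would be 17–33% of a 3–6 patient cohort.

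These sizes assume equal lesions with the others unchanged and, for masking, a halved lesion; they are illustrations, not forecasts. The documents do not say how often palliative radiation would fall in the gap. The consequence is confined to exploratory BOR and PFS and any expansion decision that draws on them. DLT counts, MTD and OID do not use tumor response and are unaffected.

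**What to change.** Leave the washout as written and change scan timing and lesion classification only.

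- **Table 2 footnote f and 7.2:** state that, where palliative radiation is given during screening, the baseline tumor assessment is performed after the last fraction. Radiation must end at least 14 days before first dose, so the later scan still fits the 28-day window.
- **Appendix II:** state that, if a lesion has nevertheless been irradiated between the baseline scan and C1D1, it is classed as non-target before C1D1 and the baseline sum is recalculated without it. No repeat scan is then needed while other target lesions remain. If it was the only target lesion, either the baseline scan is taken after radiation, or the patient is treated as having no measurable disease for the Efficacy Evaluable Population.

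The rule covers only lesions irradiated in the gap, not every lesion ever irradiated. A post-radiation scan closes the date gap but cannot remove shrinkage that continues after it, so radiation site and dates should be listed beside the lesion measurements.

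The cost is a few sentences, an occasional rescheduled scan and an occasional lost target lesion. The rule has to be in place before a patient is dosed, because a post-radiation baseline cannot be recovered afterwards.
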